### **2.7.1.1 Adverse events of special interest / grouping of AEs**

An adverse event of special interest is a grouping of adverse events that are of scientific and medical concern specific to compound MBG453. These groupings are defined using MedDRA terms, SMQs (standardized MedDRA queries), HGLTs (high level group terms), HLT (high level terms) and PTs (preferred terms). Customized SMQs (Novartis MedDRA queries, NMQ) may also be used. A NMQ is a customized group of search terms which defines a medical concept for which there is no official SMQ available or the available SMQ does not completely fit the need. It may include a combination of single terms and/or an existing SMQ, narrow or broad. These searches will be defined in the eCRS (electronic Case Retrieval Strategy) in the DMS (Document Management System) and a listing of search terms will be provided in the CSR.

For each specified AESI, the number (%) of subjects with at least one event of the AESI occurring during on treatment period will be summarized together with the individual preferred terms in that grouping. In addition, number (%) of subjects with at least one AESIs by maximum CTC grade, related AESIs, serious AESIs as well as action taken and outcome of the respective AESI will be summarized.

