6.5.4 Follow-up for toxicities

Subjects whose treatment is interrupted or permanently discontinued due to an AE or clinically significant laboratory value, must be followed-up at least once a week (or more frequently if required by institutional practices, or if clinically indicated) for 4 weeks, and subsequently at approximately 4-week intervals, until resolution or stabilization of the event, whichever comes first. Appropriate clinical experts should be consulted as deemed necessary.

All subjects must be followed up for AEs (including irAEs and SAEs) for 30 days following the last dose of venetoclax or azacitidine (whichever was later) and 150 days following the last dose of MBG453, whichever is later.

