## **2.7 Safety analyses**

Safety analyses will be summarized for the safety set and by dose level of MBG453 (400 mg Q4W, 800 mg Q4W) and for all subjects (“All subjects” column).

Safety summaries (tables, figures) include only data from the on-treatment period with the exception of baseline data which will also be summarized where appropriate (e.g. change from baseline summaries). In addition, a separate summary for death including on treatment and post treatment deaths will be provided. In particular, summary tables for adverse events (AEs) will summarize only on-treatment events, with a start date during the on-treatment period (treatment-emergent AEs).

The overall observation period will be divided into three mutually exclusive segments:

1. Pre-treatment period: from day of subject’s informed consent to the day before first administration of study treatment
2. On-treatment period: from date of first administration of study treatment to 30 days after date of last administration of study treatment
3. Post-treatment period: any observation starting at day 31 after last administration of study treatment

An overall safety period will be defined from date of first administration of study treatment to 150 days after the last dose of MBG453.

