### **2.7.1 Adverse events (AEs)**

Summary tables for adverse events (AEs) will include all AEs that started or worsened during the on-treatment period. When specified, some AEs summaries will include all AEs occurring during the overall safety period.

The number (and percentage) of subjects with treatment emergent adverse events will be summarized by primary system organ class (SOC), preferred term (PT) and maximum severity. A subject with multiple occurrences of an AE will be counted only once in the respective AE category. A subject with multiple CTCAE grades for the same PT will be summarized under the maximum CTCAE grade recorded for the event. AEs will be assessed according to the Common Terminology Criteria for Adverse Events (CTCAE) version 5.0.

In the AE summaries, the primary SOC will be presented alphabetically, and the PT will be sorted within primary SOC in descending frequency. The sort order for the PT will be based on their frequency in the “overall” column (combining the two dose levels of MBG453). The summaries will show ‘All grades’ (including AEs with missing grade) and ‘Grades  $\geq$  3’.

The following adverse event summaries will be produced selecting all or a subset of AEs depending on seriousness, relationship to study treatment, outcome or action taken:

- AEs (by SOC and by PT) and separately those considered related to study treatment
- SAEs and separately those considered related to study treatment
- SAEs with number of occurrences (an occurrence is defined as  $>1$  day between start and prior end date of record of same PT)
- Non-SAEs
- SAEs with fatal outcome and separately those considered related to study treatment
- AEs leading to permanent study treatment discontinuation by study treatment component (AEs leading to MBG453 permanent discontinuation, AEs leading to azacitidine permanent discontinuation, AEs leading to venetoclax permanent discontinuation and AEs leading to permanent discontinuation of any of the 3 study treatment components)
- AEs leading to dose adjustment/interruption
- AEs requiring additional therapy
- COVID-19 related adverse events by MedDRA COVID-19 (SMQ) terms.

In addition, all AEs and SAE by SOC and PT will be also provided on the overall safety period. All reported AEs will be listed and those that started during the pre-treatment, on-treatment and post-treatment period will be flagged.

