#### **Date of last administration of study treatment (combination)**

The date of last administration of study treatment (or start date of study treatment) is defined as the last date when the last non-zero dose of any last component of the study treatment (MBG453, azacitidine or venetoclax) is administered.

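### AESI tables cover only the on-treatment period although events are collected to 150 days after MBG453, and the overall safety period can end before the on-treatment period does

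*SAP*

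**What the plan says.** **AESI tables.** SAP 2.7.1.1 defines AESIs as groupings of concern particular to MBG453 and counts subjects with "at least one event of the AESI occurring during on treatment period will be summarized". The breakdowns by maximum grade, relatedness, seriousness, action taken and outcome name no period.

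**On-treatment period.** SAP 2.7 defines it as "from date of first administration of study treatment to 30 days after date of last administration of study treatment". SAP 5.1 takes the last administration of the combination as "the last date when the last non-zero dose of any last component of the study treatment", so the 30 days run from whichever of the three drugs is given last, not from MBG453.

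**Default and exception.** SAP 2.7 sets the default: "Safety summaries (tables, figures) include only data from the on-treatment period", apart from baseline data and a separate summary of deaths. SAP 2.7.1 allows an exception: "When specified, some AEs summaries will include all AEs occurring during the overall safety period". The exception is used there once: "In addition, all AEs and SAE by SOC and PT will be also provided on the overall safety period". SAP 2.7.1.1 does not invoke it.

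**Overall safety period.** SAP 2.7: "An overall safety period will be defined from date of first administration of study treatment to 150 days after the last dose of MBG453". Protocol 12.5.2 has the same definition.

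**Collection.** Protocol 6.5.4 follows all subjects for AEs, naming irAEs and SAEs, to 30 days after the later of venetoclax and azacitidine and "150 days following the last dose of MBG453, whichever is later".

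**The concern.** The AESI tables are the one safety display built around the investigational drug, yet their window is shorter than the collection window that the protocol attaches to that drug. SAP 2.7.1 applies the longer window to the general AE and SAE tables, and SAP 2.8.3 uses 150 days after the last MBG453 dose as the limit for immunogenicity samples. Protocol 4.6 calls immune-related events an anticipated risk of MBG453. An AESI that starts after the on-treatment cut-off but within 150 days of MBG453 would be collected and then counted in no AESI table. SAP section 1 plans a single final CSR, so no other planned report would fill the gap.

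The definition of the overall safety period raises a second problem. Protocol 6.5.3 lets a subject continue on only the tolerated drugs. If MBG453 is the drug dropped and the others go on long enough, a period that is meant to contain the on-treatment period ends before it.

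**Working it through.** There is no stated figure to reproduce. The check compares the windows, all counted in days from the last MBG453 dose.

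**Inputs**
- L = days from the last MBG453 dose to the last dose of any study drug. The documents give no distribution for L, so the values below are assumptions.
- On-treatment period, and so the AESI tables, ends at day L + 30 (SAP 2.7, 2.7.1.1, 5.1).
- Overall safety period ends at day 150 (SAP 2.7).
- Collection ends at the later of day 150 and 30 days after the last azacitidine or venetoclax dose (Protocol 6.5.4). When one of those drugs is given last, the second limit is day L + 30.

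**Limb 1: days collected but in no AESI table**

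Gap = max(0, 150 − (L + 30)) = max(0, 120 − L).

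| Assumed L | How it could arise | AESI tables end (day) | Gap (days) |
|---|---|---|---|
| 0 | MBG453 is the last drug given, for example single-agent MBG453 after CR and at least 18 cycles (Protocol 6.1.4) | 30 | 120 |
| 20 | Last MBG453 on Day 8, venetoclax to Day 28 of the same cycle: 28 − 8 = 20 | 50 | 100 |
| 120 | Other drugs continue for 120 days after MBG453 | 150 | 0 |

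At L = 0 the gap is 120/150 = 80% of the calendar days after the last MBG453 dose. That is the maximum, and it is a share of days, not of events or subjects.

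**Do other outputs fill the gap?** Late events do appear in the overall-safety-period tables by SOC and PT and in the listing of all AEs. AESI groupings, however, combine SMQs, higher-level terms, preferred terms and custom queries (SAP 2.7.1.1), so one grouping can span several preferred terms. A subject with two of those terms is counted in both rows, so adding rows does not give the number of subjects with at least one AESI. The SOC/PT tables also lack the AESI breakdowns by action and outcome. The SAP listing flags events as pre-, on- or post-treatment, so a late event is marked only as post-treatment. Protocol 12.5.2 would instead flag the overall safety period.

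**Limb 2: on-treatment days outside the overall safety period**

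The on-treatment period ends later when L + 30 > 150, that is, when L > 120. The excess is L − 120 days. For example, with an assumed five further 28-day cycles of the other drugs, L = 5 × 28 = 140 and the excess is 20 days. AEs starting in those days are collected and enter the on-treatment tables, but fall outside the overall AE and SAE tables.

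**The case against.** The strongest reply is that little is lost. Late events are collected, tabulated by SOC and PT over 150 days, and listed. SAP 2.7.2 summarizes all deaths, post-treatment ones included. The AESI search terms go into the CSR, so a reader can map late preferred terms to groupings. The scheme also follows Protocol 12.5.2, and the 150 days in Protocol 6.5.4 is a collection rule rather than a tabulation rule, so the documents do not contradict each other on the AESI tables. All of this stands, and it limits the point to the AESI display. It does not remove the point, because subject-level AESI incidence and its breakdowns over 150 days cannot be rebuilt from the planned tables.

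A second reply is that late ascertainment is weaker. After the 30-day visit, contact is by telephone at days 90 and 150 unless the patient happens to attend (Protocol 9.1.1.1). Once new antineoplastic therapy starts, only suspected-related events are collected. For subjects moved to an alternative setting, collection stops at EOT (Protocol 10.1.1). This also stands. It is a reason to footnote the added tables and to keep the on-treatment ones, and it applies equally to the 150-day AE and SAE tables already planned.

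A third reply is that limb 2 loses no AESI data: when L exceeds 120 the AESI tables already run past day 150. That is correct. Limb 2 is a separate fault in the overall AE and SAE tables, carried over from the protocol.

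A reader might infer that delayed immune toxicity is the main risk of MBG453 and that the AESI incidence is therefore biased low. The documents do not support that. Protocol 4.6 says neither main nor delayed. The AESI groupings are held in the case retrieval strategy, so the inclusion of immune-related events is an inference. The on-treatment incidence is not biased for what it defines; it is lower or equal only relative to a 150-day count.

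**Conclusion.** Both limbs hold, within narrow limits.

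First, AESIs starting in the last max(0, 120 − L) days of the 150 days after MBG453 are collected but enter no AESI table. The gap is at most 120 days, 100 days if venetoclax runs to the end of the last MBG453 cycle, and nil if other study treatment continues for 120 days or more. How many events this affects cannot be computed from the documents. The reading that the breakdowns by grade, relatedness, seriousness, action and outcome share the on-treatment window rests on the SAP 2.7 default, since SAP 2.7.1.1 does not state their period.

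Second, when L exceeds 120, the overall safety period closes L − 120 days before the on-treatment period, and the overall AE and SAE tables omit on-treatment events. This departs from the later-of-two-limits rule in Protocol 6.5.4.

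No primary endpoint, decision rule or data collection is affected. This is a cheap improvement to safety reporting, not a flaw that threatens the trial's conclusions.

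**What to change.** 1. In SAP 2.7.1.1, add the AESI tables (incidence, maximum grade, related, serious, action taken, outcome) on the overall safety period beside the on-treatment ones, and state the period for every AESI table. The added set should supplement the on-treatment set, not replace it.
2. In SAP 2.7, end the overall safety period at the later of 150 days after the last MBG453 dose and 30 days after the last azacitidine or venetoclax dose, matching the existing follow-up rule in Protocol 6.5.4. Because Protocol 12.5.2 uses the MBG453-only definition, record the change in SAP section 4, which now lists none.
3. Footnote the added tables: after new antineoplastic therapy starts only suspected-related events are collected, and collection ends at EOT for subjects moved to an alternative setting.

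The cost is one repeated set of AESI tables, one redefined end date and a footnote. No new data are needed. The drawback is that the later part of the 150 days mixes complete and selective ascertainment, which the footnote discloses.

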## **2.7.2 Deaths**

Separate summaries for on-treatment and all deaths (including post-treatment deaths not in the AE CRF but in the survival CRF) will be produced showing deaths reasons by primary reason and PT. All deaths will be listed, post treatment deaths will be flagged. A separate listing of deaths prior to starting treatment will be provided for all screened subjects.

## **2.7.3 Laboratory data**

Grading of laboratory values will be assigned programmatically as per National Cancer Institute (NCI) Common Terminology Criteria for Adverse Events (CTCAE) version 5.0. The calculation of CTCAE grades will be based on the observed laboratory values only, clinical assessments will not be taken into account.

CTCAE Grade 0 will be assigned for all non-missing values not graded as 1 or higher.

For laboratory tests where grades are not defined by CTCAE version 5.0, results will be categorized as low/normal/high based on laboratory normal ranges.

For laboratory tests where grades are defined by CTCAE v5.0:

- Shift tables using CTCAE v5.0 grades to compare baseline to the worst on-treatment value

Liver function parameters of interest are total bilirubin, ALT, AST and alkaline phosphatase. The number (%) of subjects with worst post-baseline values as per Novartis Liver Toxicity guidelines will be summarized.

For hematology parameters, trends over time (baseline and on-treatment timepoints) will be displayed via boxplots and corresponding tables displaying the summary statistics will be produced.

All CTCAE Grade 3 or 4 laboratory toxicities will be listed.

## **2.7.4 Other safety data**

Safety data listed in this section will be analyzed and summarized for the safety set and presented by dose level of MBG453 (400 mg Q4W, 800 mg Q4W) and for all subjects (“All subjects” column), and by visit/sampling timepoint.

### **2.7.4.1 ECG and cardiac imaging data**

ECG are collected as 12-lead triplicate using the ECG machines supplied by the central laboratory and then transmitted electronically to the central laboratory for central review by an independent reviewer. These central ECGs are done at screening, C1D1 pre-dose, C1D8 post-dose, C3D8 post-dose and at end of treatment; however, additional ECGs can be done if clinically indicated.

Notable ECG values during on-treatment period in subjects with normal values at baseline (for the respective QTc value) will be summarized using the following criteria:

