12.5.2 Safety endpoints

Safety analyses will be summarized for the safety set and by dose level of MBG453.

Safety summaries (tables, figures) include only data from the on-treatment period with the exception of baseline data which will also be summarized where appropriate (e.g. change from baseline summaries). In addition, a separate summary for death including on treatment and post treatment deaths will be provided. In particular, summary tables for adverse events (AEs) will summarize only on-treatment events, with a start date during the on-treatment period (treatment-emergent AEs).

The overall observation period will be divided into three mutually exclusive segments:

1. Pre-treatment period: from day of subject's informed consent to the day before first administration of study treatment
2. On-treatment period: from date of first administration of study treatment to 30 days after date of last administration of study treatment
3. Post-treatment period: any observation starting at day 31 after last administration of study treatment

An overall safety period will be defined from date of first administration of study treatment to 150 days after the last dose of MBG453.

Adverse events

Summary tables for adverse events (AEs) will include only AEs that started or worsened during the on-treatment period. The number (and percentage) of subjects with treatment emergent adverse events will be summarized by primary system organ class, preferred term and maximum severity.

Separate summaries will be provided for study medication related adverse events, death, serious adverse events, other significant adverse events leading to discontinuation, and adverse events leading to dose adjustment.

Serious adverse events and non-serious adverse events will be tabulated. All deaths (on-treatment and post-treatment) will be summarized.

In addition, all AEs and SAEs which started during the overall safety period will be summarized. All reported AEs will be listed and those that started during the pre-treatment, overall safety period and post-treatment period will be flagged.

Vital signs

All vital signs abnormalities will be summarized by visit.

12-lead ECG

HR and QTcF will be obtained from 12-lead ECGs for each subject at screening and during the study. ECG data will be read and interpreted centrally.

Categorical analysis of QTcF interval and HR data will be based on the summary of number of subjects meeting or exceeding predefined limits.

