				
of CR/CRh and MRD negativity rate in subjects with CR/CRh as secondary endpoints; 3) Modify MRD negativity definition to request MRD-negative response (observed LAIP<0.1% via MRD samples) to be observed at or after morphological remission (bone marrow blast <5%) and update MRD analyses;
 
[REDACTED]
 

• Section 2.2: move IG analysis set from Section 2.8.3

• Section 2.3.1 add analysis on COVID-19 related protocol deviation as per new template.

• Section 2.4.1 remove analysis on cycle delayed and add analysis on cycle length by cycle.

• Section 2.4.2 remove the table for prior surgery and radiotherapies which will be listed only. Update analysis on transfusion: analyze only AML-related transfusions.

• Section 2.5.2 added to display via boxplot all assessments for disease response (incl. bone marrow, peripheral blood and extramedullary disease) and list some efficacy endpoints by subject (incl. BOR, OS, duration of response)

• Section 2.6 update to restrict the analysis of time-to-event secondary endpoints on MBG453 800mg Q4W dose level only.

• Section 2.6.1 add definitions of transfusion independence and dependence.

• Section 2.6.3 delete the rule of “two or more missing assessments” for all time-to-event endpoint analyses.

• Section 2.7.3 remove the shift tables for laboratory tests where grades are not defined by CTCAE v5.0.

• Section 2.7.4 add notable PR and QRS criteria in Table 2-4; Update vital signs

Date	Time point	Reason for update	Outcome for update	Section and title impacted (Current)

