				
section to state that all patients will be analyzed regardless of their baseline value.
 

• Section 2.8 specify the analysis of PK endpoints by dose level of MBG453. Remove analysis for PK parameters and DDI.

• [REDACTED]

• [REDACTED]

• [REDACTED]

• [REDACTED]

• [REDACTED]

• [REDACTED]

• Appendix

- Update derivation of date of last exposure to investigational drug (MBG453), azacitidine, venetoclax and study treatment

- Add the derivations of cumulative dose, dose intensity and relative dose intensity of venetoclax

- Add the derivations of start/end date of a treatment cycle and cycle length

- [REDACTED]

- [REDACTED]

- Add the rules of derivation on last contact date

- Add ELN risk stratification categories (both 2017 and 2022) and the derivation algorithms

- Add ELN 2022 response categories in AML patients and its detailed derivation rules used for CRh-involved endpoints and analyses

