#### **General analysis conventions**

Qualitative data (e.g., gender, race) will be summarized by means of contingency tables; a missing category will be included as applicable. Percentages will be calculated using the number of subjects in the relevant population or subgroup as the denominator.

Quantitative data (e.g., age, body weight) will be summarized by appropriate descriptive statistics (e.g. mean, standard deviation, median, 25th and 75th percentiles, minimum, and maximum).

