**Table 2-4 Notable ECG values**

ECG parameter (unit)	Clinically notable criteria
QTcF (ms)	Increase >30 and <=60 ms Increase >60 ms New >450 to <=480 ms New >480 to <=500 ms New >500 ms
QT (ms)	Increase >30 to <=60 ms Increase >60 ms New >450 to <=480 ms New >480 to <=500 ms New >500 ms
HR (bpm)	Increase >25% and HR >100 bpm Decrease >25% and HR <50 bpm
PR (ms)	Increase from baseline >25% and to a value > 200 ms New value of > 200 ms
QRS (ms)	Increase from baseline >25% and to a value > 120 ms New values of QRS > 120 ms

In addition, local ECGs are performed but not used for summary of QTc values. If abnormalities are observed based on these local ECGs, these abnormalities are to be reported and thus summarized as AEs.

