#### 2.7.4.2 Vital signs

Notable vital sign values during on-treatment period will be summarized using the following criteria:

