## 4. Change to protocol specified analyses

Not applicable.

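### The notable-ECG summary is confined to subjects with a normal baseline QTc, but normal is undefined and subjects with a raised baseline can drop out of the QTcF rows

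*SAP*

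**What the plan says.** Incidence of notable ECG abnormalities is part of a secondary safety endpoint (protocol Table 2-1, SAP Table 1-1), with no subset of subjects named.

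- Protocol 12.5.2 places safety summaries in the safety set and says of the ECG: "Categorical analysis of QTcF interval and HR data will be based on the summary of number of subjects meeting or exceeding predefined limits".
- SAP 2.7.4, the parent section for ECG and vital signs, also names the safety set.
- SAP 2.7.4.1 then narrows the ECG table: "Notable ECG values during on-treatment period in subjects with normal values at baseline (for the respective QTc value) will be summarized".
- SAP Table 2-4 covers QTcF, QT, HR, PR and QRS. Its QTcF rows are "Increase >30 and <=60 ms Increase >60 ms New >450 to <=480 ms New >480 to <=500 ms New >500 ms".
- SAP 2.7.4.2 carries no baseline condition for vital signs: "Notable vital sign values during on-treatment period will be summarized using the following criteria". The document history for version 2.0 describes that update as one "section to state that all patients will be analyzed regardless of their baseline value". For the ECG the same entry records only an instruction to "add notable PR and QRS criteria in Table 2-4; Update vital signs", the last words of which lead into the vital-signs change.
- SAP 5.1 defines which assessment is the safety baseline. It does not say which values are normal. The low/normal/high rule in SAP 2.7.3 is for laboratory tests.

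**The concern.** The restriction decides who can appear in the table, so an undefined term in it leaves both numerator and denominator open. Two programmers could follow the SAP and produce different tables.

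On the plain wording, the subjects removed are those who start with a longer QTc. They can have a large further increase or cross a higher limit, and these are the events the table exists to count. The trial can contain such subjects. Exclusion criterion 14b in protocol 5.2 bars a screening QTcF above 470 ms, so values above 450 and up to 470 ms are eligible. The ECG on Cycle 1 Day 1 before dosing can also be the baseline under SAP 5.1, and no limit applies to it.

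The scope is unclear as well. The parenthesis in the SAP sentence mentions QTc only, and of the five parameters in Table 2-4 only QTcF is a QTc value. Whether the condition reaches QT, HR, PR and QRS cannot be settled from the text.

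**Working it through.** The plan gives no figure to reproduce, so the check applies the stated rows to example subjects.

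**Inputs.** QTcF rows: SAP Table 2-4. Screening limit of 470 ms: protocol 5.2, criterion 14b. Normal taken as QTcF of 450 ms or less: an assumption, inferred from the lowest New limit in Table 2-4. Worst-value counting: also an assumption.

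**Step 1: example subjects.**

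| Baseline | Worst value | Change | Rows met | Counted with a 450 ms cut-off | Counted row by row |
|---|---|---|---|---|---|
| 450 ms | 520 ms | 520 − 450 = +70 | Increase >60; New >500 | both | both |
| 460 ms | 530 ms | 530 − 460 = +70 | Increase >60; New >500 | neither | New >500 counted; Increase >60 not settled |

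The two subjects have the same change and reach the same top band. A 10 ms difference in baseline decides whether they appear under the fixed cut-off.

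**Step 2: most that one subject can lose.** The two Increase bands (>30 to 60 ms, and >60 ms) exclude each other, so at most 1 applies. The three New bands also exclude each other, so at most 1 applies. The maximum is 1 + 1 = 2 rows on a worst-value count. For a baseline above 450 and up to 470 ms the lowest New band cannot be newly met, so any New row lost is >480 to 500 ms or >500 ms.

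**Step 3: row-by-row reading.** Each New row has its own lower limit (450, 480, 500 ms), and a baseline at or below that limit is what makes the value new. Those rows are then sound. The Increase rows have no absolute limit against which a baseline could be normal, so they remain unresolved.

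**Step 4: a different cut-off.** If normal meant 470 ms or higher, no subject whose baseline is within the screening limit would be lost.

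**Step 5: direction of the percentage.** SAP 2.1 says: "Percentages will be calculated using the number of subjects in the relevant population or subgroup as the denominator". The restricted group is therefore a possible denominator. Illustration with 85 subjects at 800 mg (SAP section 1) and assumed values: a = 2 events among normal-baseline subjects, k subjects with a raised baseline, m of them with an event.

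- Restricted, a/(85 − k): 2/80 = 2.5% (k = 5); 2/75 = 2.7% (k = 10); 2/65 = 3.1% (k = 20).
- Unrestricted, (a + m)/85: 2/85 = 2.4% (m = 0); 3/85 = 3.5% (m = 1).

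The restricted percentage is higher with m = 0 and lower with m = 1. The two are equal when m/k = a/(85 − k). With the 450 ms cut-off, the count of subjects can only fall.

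**The case against.** The best defence is that the parenthesis refers to the respective value and so points to row-by-row use. The New rows need a baseline condition to mean anything, and on this reading they are correct. That stands, and it reduces the problem to the Increase rows. It does not say what normal means for a change-from-baseline row, or whether the condition covers the other four parameters.

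A reader might infer an undeclared change to the protocol, because SAP section 4, headed "Change to protocol specified analyses", is marked as not applicable. The documents do not support that firmly. Protocol 12.5.2 gives no limits, no denominator and no rule for subjects already abnormal at baseline, so the SAP can fairly be said to supply this detail. The firmer tension is inside the SAP, between the safety set in 2.7.4 and the subset in 2.7.4.1.

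A reader might also infer that a raised-baseline subject loses most of the five QTcF rows. Several rows could apply to such a subject, but the bands are mutually exclusive, so no more than two are lost on a worst-value count.

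The vital-signs change proves little by itself. No document requires the two summaries to match, and leaving the ECG rule in place may have been deliberate.

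Safety capture elsewhere also limits the harm. Protocol 8.4.2 requires new or worsened clinically significant ECG findings to be recorded as AEs, and protocol 6.5.4.4 triggers follow-up at QTcF above 480 ms or a rise above 60 ms without regard to whether baseline was normal. Neither replaces the categorical count.

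**Conclusion.** The concern holds as a minor point. SAP 2.7.4.1 limits the ECG table by an undefined baseline condition that its parent section and protocol 12.5.2 do not contain. With a 450 ms cut-off, which is inferred and not stated, subjects with an eligible baseline above 450 and up to 470 ms are missing from the QTcF Increase rows and the higher New bands, at a cost of at most one row of each kind per subject on a worst-value count. Read row by row, only the Increase rows are affected. The reach to QT, HR, PR and QRS is unclear.

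The documents do not give the number of subjects with a raised baseline, and it may be zero. Nor do they support a claim that the reported percentage is biased in a known direction. The effect is confined to one descriptive table. The primary CR analysis is untouched.

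**What to change.** Delete the normal-baseline restriction from SAP 2.7.4.1 and state the denominator by type of row:

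- **Change-based rows** (QTcF and QT Increase rows; HR, PR and QRS change rows): all safety-set subjects with a baseline and a post-baseline value.
- **New rows:** subjects whose baseline is at or below that row's lower limit, which is 450, 480 or 500 ms for QTcF and QT, 200 ms for PR and 120 ms for QRS.
- **Display:** n/N for every row.

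If the sponsor prefers to keep the restriction, define normal for each parameter, say which rows it governs, and state the denominator.

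The cost is a short wording change and row-specific denominators in one table. No new data are needed. Denominators will differ between rows, and percentages may shift slightly in either direction.
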